1 INTRODUCTION AND BACKGROUND INFORMATION

1.1 Background

Despite advances in treatment, approximately 70% of high-risk cardiovascular patients do not achieve low-density lipoprotein cholesterol (LDL-C) goals, and as many as 10% of hypercholesterolemic patients do not tolerate statins.^{1,2} Elevated LDL-C levels are associated with cardiovascular disease, including myocardial infarctions and strokes, and drugs such as statins that lower LDL-C also reduce cardiovascular morbidity and mortality. Insulin resistant type 2 diabetics have a high incidence of atherosclerosis, and 65% to 80% of diabetics die of macrovascular cardiovascular disease.³ Diabetes is associated with a dyslipidemia characterized by non-alcoholic fatty liver disease (NAFLD), elevated triglycerides, atherogenic low-density lipoprotein particles and reduced high-density lipoprotein cholesterol (HDL-C) that is not well treated by existing therapies.^{4,5}

In large part because of the worldwide obesity and diabetes epidemic, the prevalence of NAFLD has increased dramatically with prevalence rates of approximately 25% of the US population.⁶ Non-alcoholic fatty liver disease may lead to non-alcoholic steatohepatitis (NASH), a more serious liver disease that can lead to liver cirrhosis and increased cardiovascular disease. Non-alcoholic steatohepatitis was described more than 30 years ago and is characterized by findings on liver biopsy including fatty changes with lobular hepatitis (ballooning and inflammation) in the absence of history of alcoholism. The histologic components of steatosis, inflammation, and ballooning degeneration may be accompanied by various degrees of fibrosis.

MGL-3196 is a liver-directed, orally active, partial agonist for the thyroid hormone receptor (THR), with approximately 28-fold selectivity for the beta receptor compared to the active thyroid hormone, triiodothyronine (T3). Selectivity for a thyroid agonist at thyroid hormone receptor beta (THR- β) isoform, the predominant liver thyroid hormone receptor, has the potential of providing metabolic benefits of thyroid hormone that are mediated in the liver, while avoiding unwanted systemic actions of thyroid hormone in heart and bone that are largely mediated through THR alpha (THR- α).⁷

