 - o Previous liver biopsy consistent with NASH.

Note: Assessment of the above, or other objective modalities suggested by PI, will occur. The choice of additional procedures, performed during the screening period prior to the screening MRI and liver biopsy, may include calculation of FIB-4, APRI, NAFLD fibrosis scores, and/or performance of fibroscan and/or CAP.

5. Must have confirmation of $\geq 10\%$ liver fat content on MRI-PDFF;

Note: Patients with a liver fat content $>9\%$ but $< 10\%$ on MRI-PDFF and who are highly likely to have NASH as determined by Medical Monitors on biopsy may be included in the study but the total may not exceed 10% of the total study population;

6. Biopsy-proven NASH:

- Must have had prior liver biopsy within 180 days of randomization with fibrosis stage 1 to 3 and a NAS of ≥ 4 with at least a score of 1 in each of the following NAS components:
 - Steatosis (scored 0 to 3),
 - Ballooning degeneration (scored 0 to 2), and
 - Lobular inflammation (scored 0 to 3); and

Note 1: Patients who have clear ballooning with fibrosis but no inflammation or patients who have clear inflammation with fibrosis but no ballooning or patients with clear NASH without fibrosis may be included in the study but the total may not exceed 10% of the total study population;

Note 2: If a historical biopsy is to be used, patients must have had no significant change in metabolic status (diabetes control, lipid metabolism, and/or $>5\%$ weight loss), significant change in diabetes medication, or change in use of medications listed in Exclusion #11 since the biopsy;

Note 3: If a historical biopsy is not available, patients must have confirmation of $\geq 10\%$ liver fat content on MRI-PDFF prior to undergoing liver biopsy. However, if, in the opinion of the patient's physician, the patient would benefit from and be advised to obtain a liver biopsy, the patient may undergo liver biopsy prior to MRI-PDFF;

7. Must have documented historical (3 weeks to 6 months prior to the study entry) ALT and AST levels consistent with the screening ALT and AST values. This consistency is established based on the following:

- If the historical and screening ALT and AST values are both $\leq 1.5 \times$ the upper limit of normal (ULN), there is no limit to the difference between the values

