6. Prior or planned (during the study period) bariatric surgery (eg, gastroplasty, roux-en-Y gastric bypass);
7. Type 1 diabetes;
8. Uncontrolled Type 2 diabetes defined as:
 - Hemoglobin A1c $\geq 9.5\%$ at screening (patients with HbA1c $\geq 9.5\%$ may be rescreened),
 - Insulin dose adjustment $> 10\%$ within 60 days prior to enrollment,
 - Requirement for glucagon-like peptide analogue (unless on a stable dose ≥ 6 months prior to screening) or a complex oral anti-diabetic (OAD) regimen (3 or more OADs) (unless the OAD is stable and HbA1c $< 8\%$), or
 - History of severe hypoglycemia (symptomatic hypoglycemia requiring outside assistance to regain normal neurologic status);

Note: Individual diabetes regimens will be reviewed by Investigator and may be adjusted based on American Diabetes Association guidelines;

9. Use of the following lipid-modifying therapies: fibrates except fenofibrate taken at night for at least 2 weeks prior to randomization and during the study, niacin, proprotein convertase subtilisin/kexin type 9 inhibitors, and bile acid sequestrants. Atorvastatin up to 20 mg and

rosuvastatin up to 10 mg and pravastatin up to 20 mg, on stable dose for at least six weeks prior to randomization (four weeks prior to MRI), are allowed. Other statins are excluded. Stable doses for at least three months prior to randomization of fish oils (omega-3 fatty acids, eicosapentaenoic acid, and docosahexaenoic acid), fenofibrate and ezetimibe are allowed;

Note: Very infrequently, given that lipid levels are blinded to investigators and study personnel, where indicated statin and other allowed lipid therapies may be modified or initiated after enrollment in the study. Statin doses may be decreased during the study for tolerability or safety issues. Statin doses should be taken in the evening for at least two weeks prior to randomization and for the duration of the study.

10. Use of obeticholic acid, ursodeoxycholic acid (Ursodiol® and Urso®), high dose vitamin E (>400 IU/day) unless on stable dose of vitamin E >400 IU/day for at least 6 months at the time of liver biopsy, or pioglitazone within 90 days prior to enrollment or since screening biopsy, whichever is longer.
11. Presence of cirrhosis on liver biopsy (stage 4 fibrosis);
12. Platelet count <140,000/mm³;
13. Clinical evidence of hepatic decompensation which may be:

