9.15 Liver Biopsy

Patients will undergo liver biopsy at the Screening Visit (Week -6 to 0) only in the event that the patient does not have available liver biopsy within 180 days of randomization. If a historical biopsy is to be used, patients must have had no change in metabolic status (diabetes, lipid metabolism, and/or >5% weight gain or loss) or change in diabetes medications. If a historical biopsy is not available, patients must have confirmation of $\geq 10\%$ liver fat content on MRI-PDFF prior to undergoing liver biopsy. However, if, in the opinion of the patient's physician, the patient would benefit from and be advised to obtain a liver biopsy, the patient may undergo liver biopsy prior to MRI-PDFF. All patients will undergo liver biopsy at Week 36. Patients may undergo liver biopsy at the Early Termination Visit based on the discretion of the Investigator. Liver biopsies will be read by 1 central reader. Reading will include assessment of fibrosis stage, portal inflammation, and NAS.

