#### 2.3.1.2 Liver Biopsy Assessments

- NASH Biopsy Responders:
  - The number and percentage of patients achieving a 1-point reduction in NAS;
  - the number and percentage of patients achieving a 2-point reduction in NAS at 36 weeks;
  - the number and percentage of patients achieving a 2-point reduction in NAS at 36 weeks; and either  $\geq 1$  point reduction in lobular inflammation or  $\geq 1$  point reduction in hepatocellular ballooning; and
  - the number and percentage of patients achieving a 2-point reduction in NAS at 36 weeks; and no worsening of fibrosis.
- NASH Component Responder definition (only requires one or more criteria):
  - reduction in hepatocellular steatosis; or
  - reduction in lobular inflammation; or
  - reduction in hepatocellular ballooning.

- Fibrosis Responders:
  - the number and percentage of patients achieving  $\geq 1$  stage reduction in fibrosis;
  - the number and percentage of patients achieving  $\geq 1$  stage reduction in fibrosis; and no worsening of NAS; and
  - the number and percentage of patients achieving  $\geq 2$  stage reduction in fibrosis.
- NASH Resolution Responder Definition (requires both criteria):
  - lobular inflammation = 0 or 1; and
  - hepatocellular ballooning = 0.
- NASH Resolution Responders with at least a 2-point reduction in NAS at Week 36.
- Other exploratory NASH Resolution Responders:
  - [REDACTED]
  - [REDACTED]
- The number and percentage of patients achieving a change in NASH diagnosis (ie, from definite NASH to not-NASH based on histology) from baseline to Week 36.

Other liver biopsy analyses include:

- [REDACTED]
- The change in portal inflammation from baseline at 36 weeks; and
- [REDACTED]
- Correlation of reduction of liver fat on MRI-PDFF at 12 and 36 weeks with improvement or resolution of NASH on liver biopsy.

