### 3.7.3 Analyses of Liver Biopsy Results

All endpoints will be summarized and analyzed based on the mITT population for MGL-3196 80 mg versus placebo. For liver biopsy, mITT includes only patients with both eligible baseline and Week 36 biopsies. Since this is for exploratory purpose, no multiplicity will be controlled.

Responder variables at Week 36 include:

- NASH Biopsy Responders:
  - The number and percentage of patients achieving a 1-point reduction in NAS;
  - the number and percentage of patients achieving a 2-point reduction in NAS at 36 weeks;
  - the number and percentage of patients achieving a 2-point reduction in NAS at 36 weeks; and either  $\geq 1$  point reduction in lobular inflammation or  $\geq 1$  point reduction in hepatocellular ballooning; and
  - the number and percentage of patients achieving a 2-point reduction in NAS at 36 weeks; and no worsening of fibrosis.
- NASH Component Responder definition (only requires one or more criteria):
  - reduction in hepatocellular steatosis; or
  - reduction in lobular inflammation; or
  - reduction in hepatocellular ballooning.
- Fibrosis Responders:
  - the number and percentage of patients achieving  $\geq 1$  stage reduction in fibrosis;
  - the number and percentage of patients achieving  $\geq 1$  stage reduction in fibrosis; and no worsening of NAS; and
  - the number and percentage of patients achieving  $\geq 2$  stage reduction in fibrosis.
- NASH Resolution Responder Definition (requires both criteria):
  - lobular inflammation = 0 or 1; and
  - hepatocellular ballooning = 0.

- NASH Resolution Responders with at least a 2-point reduction in NAS at Week 36.
- Other exploratory NASH Resolution Responders:

- The number and percentage of patients achieving a change in NASH diagnosis (ie, from definite NASH to not-NASH based on histology) from baseline to Week 36.

The definite NASH based on histology is specified as: fibrosis stage 1 to 3 and a NAS of  $\geq 4$  with at least a score of 1 in each of the following NAS components:

- Steatosis (scored 0 to 3),
- Ballooning degeneration (scored 0 to 2), and
- Lobular inflammation (scored 0 to 3).

Fisher's exact test will be used to compare the percentages between MGL-3196 80 mg versus placebo. Confidence intervals and p-values will also be provided.

NOTE:

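### The change-in-diagnosis biopsy responder carries the entry range of fibrosis stage 1 to 3 into Week 36, so progression from stage 3 to cirrhosis with unchanged activity scores counts as a response

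*SAP*

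**What the plan says.** SAP 2.1.3, 2.3.1.2 and 3.7.3 all list, as a count and a percentage, responders defined by "achieving a change in NASH diagnosis (ie, from definite NASH to not-NASH based on histology) from baseline to Week 36". SAP 3.7.3 then gives the one visible definition: "The definite NASH based on histology is specified as: fibrosis stage 1 to 3 and a NAS of" at least 4. It adds a condition on the components, "with at least a score of 1 in each of the following NAS components". The components are steatosis (0 to 3), ballooning (0 to 2) and lobular inflammation (0 to 3).

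This repeats inclusion criterion 6 in Protocol 4.1: "Must have had prior liver biopsy within 180 days of randomization with fibrosis stage 1 to 3 and a NAS of" at least 4, with the same component minimums. Stage 4 is on the scale and means cirrhosis. Protocol 4.2, exclusion 11, bars it at entry: "Presence of cirrhosis on liver biopsy (stage 4 fibrosis". Nothing prevents a stage 4 reading at Week 36.

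Protocol 9.15 says of the central reading: "Reading will include assessment of fibrosis stage, portal inflammation, and NAS". It names no separate diagnostic category. SAP 3.7.3 compares the arms with Fisher's exact test and reports confidence intervals and p-values. It describes the biopsy analyses as exploratory and applies no multiplicity control.

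**The concern.** An entry range and an outcome definition do different jobs. At entry, the upper limit of stage 3 keeps patients with cirrhosis out. At Week 36, the same limit means that a patient whose fibrosis has advanced past it no longer fits the description of definite NASH. If everything outside the description is not-NASH, that patient has changed diagnosis in the favourable direction. Protocol 1.1 describes NASH as "a more serious liver disease that can lead to liver cirrhosis", so the rule can count as success a course that the protocol itself presents as progression.

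The lower limit has a milder version of the same fault. A fall from stage 1 to stage 0 with NAS unchanged is recorded as loss of NASH, although steatosis, ballooning and inflammation are as they were. That is an improvement in fibrosis, which the SAP already counts under its Fibrosis Responders.

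What is at stake is the meaning of one tested row in the biopsy tables.

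**Working it through.** The documents give no figure for this endpoint, so there is none to reproduce. The check applies the rule to every possible set of scores.

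**Inputs** (SAP 3.7.3; stage 4 from Protocol 4.2). Steatosis s = 0 to 3, ballooning b = 0 to 2, lobular inflammation i = 0 to 3, fibrosis f = 0 to 4. NAS = s + b + i. Definite NASH: 1 ≤ f ≤ 3, NAS ≥ 4, and each of s, b, i ≥ 1. Not-NASH is taken as the complement, which is an inference.

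**States**
- All states: 5 × 4 × 3 × 4 = 240, which is 48 per fibrosis stage.
- With every component at least 1: 3 × 2 × 3 = 18. Only 1/1/1 (NAS 3) fails NAS ≥ 4, leaving 17 per stage.
- Definite NASH: 3 stages × 17 = 51.
- Definite NASH at stage 4: 0 of 48, although 17 of those states have NAS ≥ 4 and every component at least 1.

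**Stage 3 to stage 4.** Scores 2/2/2 at stage 3 are definite NASH. The same scores at stage 4 are not, so the patient is a responder. This holds for all 17 stage 3 states.

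Allowing any Week 36 scores, there are 17 × 48 = 816 transitions from stage 3 definite NASH to stage 4, and all 816 are responses. The number with NAS unchanged or worse is found by baseline NAS:

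| Baseline NAS | Definite-NASH states at stage 3 | Stage 4 states with NAS at least as high | Product |
|---|---|---|---|
| 4 | 3 | 29 | 87 |
| 5 | 5 | 19 | 95 |
| 6 | 5 | 10 | 50 |
| 7 | 3 | 4 | 12 |
| 8 | 1 | 1 | 1 |
| Total | 17 | | 245 |

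**Stage 1 to stage 0.** With scores unchanged, all 17 stage 1 states become not-NASH.

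**Effect of changing the rule on the 816 transitions**
- As written: 816 responders.
- Upper limit removed at Week 36: 816 − (17 × 17 = 289) = 527. The 289 still have NAS ≥ 4 and every component at least 1.
- Worsened fibrosis also counted as non-response: 0.

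Dropping the fibrosis range at Week 36 also removes the 17 stage 1 to stage 0 cases with unchanged scores.

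**Illustration of size.** These are counts of possible states, not of patients or probabilities. The documents give neither the number of stage 3 patients nor a progression rate. Assume 1 to 3 such patients in an arm, and use the Week 12 MRI counts in the Protocol's Amendment 6 summary (38 placebo, 78 active) as stand-in denominators:
- Placebo: 1/38 = 2.6 to 3/38 = 7.9 percentage points added to the responder rate.
- Active: 1/78 = 1.3 to 3/78 = 3.8 percentage points.

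**The case against.** **Standing of the endpoint.** It is one of about a dozen biopsy responder variables that SAP 3.7.3 calls exploratory. It is not among the visible primary or secondary variables in Protocol Section 7. The NASH Resolution definition (ballooning 0, inflammation 0 or 1) has no fibrosis range. All of this stands and limits the weight of the point.

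**Worsening is shown elsewhere.** SAP 3.7.3 also tabulates patients whose fibrosis improved, was unchanged or worsened, and lists "the number and percentage of patients achieving a 2-point reduction in NAS at 36 weeks; and no worsening of fibrosis". A patient who reached stage 4 would be visible there. That is true, but neither item alters responder status in the change-in-diagnosis row.

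**Not-NASH may have been meant differently.** The complement is inferred. The wording in Protocol 9.15 need not be exhaustive, the Amendment 6 summary mentions a scoring-sheet page for non-NASH findings, and neighbouring items in the SAP lists are redacted. So a pathologist's overall diagnosis cannot be excluded. But SAP 3.7.3 specifies the diagnosis by scores, and a programmer following the visible text would code the complement. If something else was intended, the SAP has to say so.

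**Stronger readings.** A reader might infer that the endpoint cannot measure what its name says, because a fall in steatosis alone, or a move from NAS 4 to NAS 3, can end definite NASH. The documents do not support treating that as an error. Protocol 1.1 includes fatty change in its description of NASH, and any cut-off can be crossed by one point. A reader might also infer that patients admitted under Note 1 of inclusion 6, who are not definite NASH at baseline, stay in the denominator without being able to respond. The SAP restricts the biopsy mITT set to eligible baseline and Week 36 biopsies without defining eligible, so the denominator is unspecified, not shown to be wrong.

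**Conclusion.** The point holds for the fibrosis range. As written, and with not-NASH read as the complement, the rule scores every move from stage 3 definite NASH to stage 4 as a response, including those with unchanged or worse NAS. It also scores a move from stage 1 to stage 0 with unchanged scores as loss of NASH. The state counts are exact given that reading.

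The number of patients affected is unknown and may be small over 36 weeks. The direction of bias is also unknown: more progression on placebo would raise the placebo rate and dilute a difference, while more on active would inflate it. A reader might infer that the rule favours the drug, but nothing in the documents shows that.

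The consequence is confined to one exploratory endpoint. It is still worth correcting, because the rule gives a wrong classification and the data needed to repair it are already collected.

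**What to change.** In SAP 3.7.3, with matching text in 2.1.3 and 2.3.1.2:

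1. Keep the present definition to identify definite NASH at baseline, and use those patients as the denominator for this endpoint.
2. At Week 36, define not-NASH as no longer meeting the activity part of the definition (NAS ≥ 4 with at least 1 in each component), without the fibrosis range.
3. Count any patient with worsened fibrosis, including any who reach stage 4, as a non-responder. The SAP already uses this condition for a 2-point NAS responder in the same list.
4. SAP 2.2.1 reports that the treatment code was revealed while the extension was ongoing. If the revision is adopted after unblinding, label it post hoc and show the result under the present SAP definition beside it.

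The cost is a few lines of SAP text and programming, with no new readings. The responder percentage may be slightly lower, since some patients who now count would not.

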## 2.3 Study Endpoints

### 2.3.1 Efficacy Variables

#### 2.3.1.1 MRI-PDFF Assessments

The primary efficacy variable is percent change in hepatic fat fraction by MRI-PDFF from baseline at 12 weeks for MGL-3196 80 mg versus placebo in patients with biopsy-proven NASH.

The other related efficacy variables with MRI-PDFF at Week 12 are:

- Change in hepatic fat fraction by MRI-PDFF from baseline;
- Proportion of patients who have 30% or more reduction in hepatic fat fraction by MRI-PDFF from baseline at Week 12, that is, the percent change from baseline to Week 12 is  $\leq -30\%$ ;
- Proportion of patients who have 5% or more absolute reduction in hepatic fat fraction by MRI-PDFF from baseline at Week 12, that is, the change from baseline to Week 12 is  $\leq -5\%$  in hepatic fat; and
- Proportion of patients who have 5% or less hepatic fat fraction by MRI-PDFF at Week 12, that is, the hepatic fat fraction measurement at Week 12 is  $\leq 5\%$ .

The efficacy variables at Week 36 include:

- Five efficacy endpoints in hepatic fat fraction by MRI-PDFF as specified in the primary Week 12 efficacy endpoint from baseline at 36 weeks for MGL-3196 80 mg versus placebo;

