### 3.7.2.1 Analyses of Percent Change

Percent change in hepatic fat fraction =  $100 \times (\text{Week 12} - \text{Baseline}) / \text{Baseline}$ .

An analysis will be performed on the percent change from baseline to Week 12 in hepatic fat fraction by MRI-PDFF. An analysis of covariance (ANCOVA) model with treatment as a factor will be analyzed. The SAS sample code is listed:

```
*****

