### 3.7.2.3 Week 12 Hepatic Fat Fraction Treatment Goals

There are three treatment goal endpoints that will be used to evaluate the treatment effect.

- % Change from baseline to Week 12 < -30% (% reduction of 30% or more),

- Change from baseline to Week 12  $< -5\%$  (absolute reduction of 5% or more), and
- Week 12 hepatic fat fraction  $< 5\%$ .

For each endpoint, a logistic regression model with treatment as a factor and baseline as a covariate will be used to compare the percentages of patients meeting the following treatment goals between the MGL-3196 versus placebo. The odds ratio, confidence interval, and p-value from the logistic regression will be provided.

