- The analyses performed on the NASH Resolutions endpoint will exclude patients with  $>9.5\%$  weight loss from Screening to Week 36 (the percent change in body weight from Screening to Week 36 is  $>-9.5\%$ ), including the patients only as secondary analyses. Conversely, other liver biopsy and study endpoints will include the patients, excluding them only as secondary analyses.

Other liver biopsy variables include:

- The change in fibrosis stage from baseline at 36 weeks; as a continuous variable and descriptively by numbers and percentages of patients in which fibrosis stage improved, was unchanged or worsened, for exploratory purposes only
- The change in portal inflammation from baseline at 36 weeks; and
- The change in parameters of NASH liver biopsy (NAS) from baseline at 36 weeks. The NAS score will also be summarized descriptively as a continuous variable for exploratory purposes only.
- Correlation of reduction of liver fat on MRI-PDFF at 12 and 36 weeks with improvement or resolution of NASH on liver biopsy.

Analyses of liver biopsy data will be performed on the mITT population for the following subgroups:

- Week 36 SHBG group ( $\geq 88\%$ ,  $<88\%$  change from baseline to mean SHBG post Week 12 through Week 36);
- Exposure group (AUC  $<2700$  ng\*hr/mL, AUC  $\geq 2700$  ng\*hr/mL);
- Baseline Fibrosis Stage 2/3;

- Weight loss from Screening to Week 36 (<5% weight loss,  $\geq 5\%$  weight loss,  $< 7\%$  weight loss,  $\geq 7\%$  weight loss,  $> 9.5\%$  weight loss);
- Baseline MRI-PDFF  $\geq 20\%$ ;
- Gender (male, female);
- Ethnicity (Hispanic or Latino, Not Hispanic or Latino );
- Stage of NASH ( $\geq 5$ ,  $< 5$ );
- PNPLA3 SNP phenotype (Homozygous, Heterozygous, negative);
- Type 2 diabetes (yes or no);
- MGL-3196 treated patients who have 30% or more reduction in hepatic fat fraction by MRI-PDFF from baseline at Week 12 and 36, that is, the percent change from baseline to Week 12 and 36 is  $\leq -30\%$  versus all Placebo treated patients;
- MGL-3196 treated patients who have 5% or more absolute reduction in hepatic fat fraction by MRI-PDFF from baseline at Week 36, that is, the change from baseline to Week 12 is  $\leq -5\%$  in hepatic fat versus all Placebo treated patients;
- MGL-3196 treated patients who have 5% or less hepatic fat fraction by MRI-PDFF at Week 12 and 36, that is, the hepatic fat fraction measurement at Week 12 and 36 is  $\leq 5\%$  versus all Placebo treated patients; and

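### The weight-loss exclusion for NASH resolution (SAP 3.7.3) is stated in symbols that select the opposite group to its words; two minor cut-off mismatches belong in the same correction

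*SAP*

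**What the plan says.** **Weight rule (SAP 3.7.3, NOTE).** "The analyses performed on the NASH Resolutions endpoint will exclude patients with" a weight loss above 9.5% from Screening to Week 36. A parenthesis then restates this as: "the percent change in body weight from Screening to Week 36 is" > -9.5%. The NOTE also fixes what the rule governs: "including the patients only as secondary analyses. Conversely, other liver biopsy and study endpoints will include the patients, excluding them only as secondary analyses". The subgroup list later in the same section uses a loss above 9.5%, in words, as one of its weight categories.

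**PDFF goals.** SAP 2.3.1.1 defines three responder endpoints with inclusive cut-offs: <= -30%, <= -5% and <= 5%. The second reads "Proportion of patients who have 5% or more absolute reduction in hepatic fat fraction by MRI-PDFF from baseline at Week 12". SAP 3.7.2.3, which specifies the logistic regression for the same goals, prints < -30%, < -5% and < 5%. Beside the second it still gives the inclusive gloss "absolute reduction of 5% or more"; the first has a similar gloss and the third has none. SAP 2.1.2 uses an inclusive sign, but covers only the 30% goal.

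**Visit.** One biopsy subgroup in SAP 3.7.3 is "MGL-3196 treated patients who have 5% or more absolute reduction in hepatic fat fraction by MRI-PDFF from baseline at Week 36, that is", and the definition then continues with the change to Week 12. The two neighbouring fat-reduction subgroups name Weeks 12 and 36 in both halves.

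**The concern.** The weight rule decides who is in the main analysis of NASH resolution, a secondary efficacy variable in Protocol Section 7. The other biopsy and study endpoints use the same group in reverse, as a secondary exclusion. A rule whose words and symbols select complementary groups leaves that set to whoever implements it.

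The PDFF mismatch means that a patient exactly on a cut-off is a responder in one section and a non-responder in the other. The visit mismatch leaves it open which scan defines the subgroup. Both are much smaller matters than the weight rule.

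**Working it through.** The plan gives no figure to reproduce on this point. The check is one of logic, followed by a sizing under stated assumptions.

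**Inputs**
- Cut-off of 9.5% and both statements of the rule: SAP 3.7.3, NOTE.
- Sign convention: SAP 3.7.2.1 gives "Percent change in hepatic fat fraction" as 100 x (Week 12 - Baseline)/Baseline, so a fall is negative. No other convention is given for weight.
- Patient numbers: 125 in the safety population and 116 with baseline and Week 12 MRI-PDFF (38 placebo, 78 MGL-3196), from the Protocol's Amendment 6 summary.
- PDFF planning values: difference from placebo of -5.5 points with SD 6, SD 35 for percent change, and expected baseline of 15% to 17% (SAP Section 4).
- Weight-change distribution: not in the documents. Assumed normal, mean 0 to -3%, SD 3 to 6 points.

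**Step 1. Words against symbols**

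| Weight change | Words (loss > 9.5%) | Symbols (change > -9.5%) |
|---|---|---|
| +5% | keep | exclude |
| 0% | keep | exclude |
| -3% | keep | exclude |
| -9.4% | keep | exclude |
| -9.5% | keep | keep |
| -9.6% | exclude | keep |
| -15% | exclude | keep |

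Except at exactly -9.5%, the two rules give opposite answers. This step needs no distributional assumption.

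**Step 2. Share excluded**

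For mean m and SD s, the words exclude Φ((-9.5 - m)/s) and the symbols exclude 1 minus that.

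| m, s | z | Words | Symbols |
|---|---|---|---|
| 0, 3 | -3.17 | 0.1% | 99.9% |
| -1, 4 | -2.13 | 1.7% | 98.3% |
| -2, 5 | -1.50 | 6.7% | 93.3% |
| -3, 5 | -1.30 | 9.7% | 90.3% |
| -3, 6 | -1.08 | 13.9% | 86.1% |

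The first and last rows are the extremes of the grid tried. If all 125 patients had both biopsies, the symbols would exclude 0.861 x 125 = 108 to 0.999 x 125 = 125 of them.

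**Step 3. PDFF cut-offs**

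The versions differ only at exactly -30%, -5 points or 5%. With PDFF recorded to 0.1 point (assumed), the chance of a tie is about density x 0.1.
- **-5 points.** Active, assumed N(-5.5, 6): 0.0066 x 78 = 0.5 patients. Placebo, assumed N(0, 6): 0.0047 x 38 = 0.2. Applying the higher rate to everyone gives 0.0066 x 116 = 0.8.
- **-30% and 5%.** One million values were simulated with baseline N(17, 5) floored at 9 and percent change N(-30, 35), with baseline and Week 12 values rounded to 0.1 point. Ties were 0.14% at -30% (0.2 of 116) and 0.44% at 5% (0.5 of 116).

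Each goal is therefore affected by fewer than one patient in expectation.

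**Step 4. Visit**

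Read together, the two halves of the 5-point subgroup name different visits. The neighbouring definitions use both visits, so the text does not show whether Week 12, Week 36 or both is meant.

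**The case against.** The strongest reply is that nobody would implement the symbols. The NOTE states the exclusion in words first, and the same section repeats a loss above 9.5% as a subgroup. Taken literally, the symbols would also make the secondary analyses of every other endpoint keep only patients who lost 9.5% or more, which is plainly not meant. SAP Section 5 puts the programming specifications in stand-alone documents finalised before database lock, so the parenthesis is not itself the code. All of this stands. A reader might infer that the plan as written removes nearly everyone from the NASH-resolution analysis. The documents do not support that: it would take literal programming of one faulty symbol, and the size rests on an assumed distribution.

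On PDFF, a reader might imagine whole-point recording, where about 5% to 7% of patients would tie at -5 points (5 to 8 of 116). Inclusion criterion 5 rules this out, because it admits patients with liver fat between 9% and 10%. Nor do the documents show that any responder count changed. Table 3.3.1 in the Amendment 6 summary is labelled with the strict sign and the inclusive gloss, and the label does not reveal which operator ran.

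It is also fair that SAP 3.7.3 calls the biopsy analyses exploratory, without multiplicity control, and that the visit slip touches one subgroup among many. What the reply does not remove is the contradiction in an operative rule. Version 1.2 was issued to reconcile endpoint definitions across 2.1, 2.3 and 3.7.3, yet the weight and visit errors remain inside 3.7.3.

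**Conclusion.** The contradiction in the weight rule is real and should be corrected, because it sits in the definition of a main analysis set. Its direction is certain from the text, given the SAP's own sign convention. Its size is conditional: about 86% to 99.9% excluded under literal symbols against about 0.1% to 14% under the words, for normal weight change with mean 0 to -3% and SD 3 to 6 points. There is no evidence that the literal reading was or would be used.

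The PDFF mismatch is minor. It concerns exact ties, likely under 1 of 116 per goal at 0.1-point recording (assumed). For the third goal, the conflict is between sections, not with words beside the symbol. The visit mismatch is a drafting error with no demonstrated effect on a conclusion. Neither would merit a separate point.

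**What to change.** 1. In the SAP 3.7.3 NOTE, change the parenthesis to < -9.5%. Patients at -9.6% are then excluded and those at -9.5%, -3%, 0% and +5% kept, in agreement with the words. Confirm that the stand-alone specifications and the code apply this rule, both in the main NASH-resolution analysis and in the secondary analyses of other endpoints.
2. In SAP 3.7.2.3, print <= -30%, <= -5% and <= 5% to match 2.3.1.1, and check which operator the Week 12 programs used.
3. In the 5-point absolute-reduction biopsy subgroup, name the same visit or visits in both halves. The sponsor has to say which is meant.

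This is five edits: one weight symbol, three PDFF symbols and one visit. The cost is a short SAP revision and a code check. Items 1 and 2 follow the SAP's own words and change no intended analysis. If the analyses have already run, the check and any deviation belong in the clinical study report, as SAP Section 1 provides.
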